7.3.3 CASI Data Security

CASI Data Security

Only authorized users with a login name and password will be able to access and open the online HIPPA-compliant online CASI platform administered survey.

7.3.4 Video Platform Description

A HIPPA-compliant video platform will be used for this study. Either Zoom or a comparable platform may be used to conduct qualitative interviews remotely and/or to enable remote enrollments. For the qualitative interviews, participants will have the option to conduct face-to-face video chat, video chat in which they can see the interviewer, but the interviewer cannot see them, or audio chat only. In order to ensure privacy, participants will be asked to complete the interview within a private room. Zoom is compatible on PCs, tablets, and smartphones; as well as maintains the option to conduct an audio conference without the video component.

End-to-end encryption: Zoom encrypts all presentation content at the application layer using the Advanced Encryption Standard (AES) 256-bit algorithm. Zoom end-to-end (E2E) chat encryption allows for a secured communication where only the intended recipient can read the secured message. Zoom uses public and private keys to encrypt the chat session with Advance Encryption Standard (AES256), and session keys are generated with device unique hardware ID to avoid data being read from other devices. This ensures that the session cannot be eavesdropped on or tampered with.

Cloud Control Infrastructure: A distributed network of low-latency multimedia routers (software) resides on Zoom's communications infrastructure. With these low-latency multimedia routers, all session data originating from the host's device and arriving at the participants' devices is dynamically switched — never stored persistently through the Zoom communications infrastructure. Zoom's communications infrastructure for real-time video, audio, and data communications resides on Zoom dedicated servers, which are housed in SSAE 16 SOC2 compliant datacenters on opposite sides of the US. Zoom sessions are completely temporary and operate analogously to the popular mobile conversation over the public mobile network. In addition to unique security benefits, Zoom's

communications infrastructure also enables an extremely scalable and highly available meeting infrastructure unrestricted by the limitations of physical data centers.

The Zoom client communicates with the multimedia router to establish a reliable and secure connection. At the time of instantiation, the Zoom client will determine the best method for communication, attempting to connect automatically using udp and tcp port 8801, 8802 and 8804 or HTTPS (port 443/TLS).

The Zoom sessions will contain identifying information, but this information will be stripped from the recorded Zoom sessions by the study team immediately post completion.

7.3.5 Back Up Recording

All qualitative interviews may also be recorded using a back-up digital audio recorder. Audio files will be erased after being transcribed and transcripts will be de-identified. All audio files will be kept confidential and stored in a locked/limited access folder on secured servers, which is only accessible to designated study staff. All members of the research team will be trained in confidentiality and have signed confidentiality agreements. A professional transcription service, experienced in the handling of confidential data, will be used to fully transcribe verbatim all audio files. Prior to receipt of the first audio file, the transcription service will be instructed to exclude from the typed transcript identifying information (e.g., a name) that may have been verbalized during the course of the interviews.

7.4 Data Submission

7.4.1 CRFs

Although Tough Talks will involve substantial online follow-up, forms on REDCap will be used to collect key study visit data (e.g., enrollment and randomization assignment), study milestones such as completion or discontinuation, study laboratory results, and adverse events (AE). During active study conduct, the study sites will maintain the CRFs within REDCap and any hard-copy CRFs will be stored in secured locations and later entered into REDCap.

7.4.2 Audio-recorded Data

Audio recorded data from the technical pilot exit interviews will initially be stored as a digital file on a secure encrypted UNC server. Exit interviews will be transcribed verbatim from the digital audio recording and de-identified by assigning unique numerical codes. After transcripts are verified by the research team and one year after the study is over, audio files will be destroyed.

All CASI data will only be identified with a unique SID and stored on a secure encrypted server by the UNC team. Only study site research staff and the research team at the University of North Carolina/Duke will have access to the data.

7.4.3 CASI Data Transmission

Only authorized users with a login and password will be able to access and open the survey through the internet site. Survey data will be stored in secured databases on a UNC server.

7.4.4 *Retention Data*

The study will use a HIPAA-compliant web-based platform entitled Study Management and Retention Toolkit (SMART), which is a SaaS (Software as a Service) based mobile application aiding studies with various aspects of participant recruitment, study implementation, and retention. The application has the ability to securely manage participant information across multiple studies and customers simultaneously, stratifying participant information by study and site. SMART includes an admin web portal and a participant facing mobile app (optional), which allows for secure messaging, study calendar management, self-scheduling by participants, secure photo uploads, and longitudinal tracking of participants from screening to study completion. The ability to designate specific roles to all SMART users allows for greater control around permissions and accessibility to participant information. Users can even be limited to a reporting only role, which allows for study oversight through real time aggregate reporting, but no access to PHI. SMART is a licensed service of the Center for AIDS Research (CFAR) at Emory University, Prevention Science Core. Utilization of the mobile app is optional and the admin web portal will fully function without it.

The following information outlines the security of the three SMART components: (1) the admin web portal, (2) the participant app, and (3) a web service that acts as a liaison between the mobile app and the study database.

Admin Web Portal: The admin web portal is a web-based application developed using Microsoft .NET technologies. It uses SQL server as backend database. The application requires two servers to host: (1) Web server [Windows server with IIS] and (2) SQL server [Standard or Enterprise version]. Both these servers are to be placed behind a firewall. Web server will have a public IP to access the server using VPN. SSL certificate is to be installed on the web server. The admin website will be rendered over SSL (https). The application uses form authentication (no integrated authentication such as AD). All passwords are stored encrypted within the database. The system will also be using database level encryption, which will prevent any copying of information from one database to another. The web application also uses an automatic logout feature after a certain period of inactivity. By default, the inactivity duration is set to three minutes.

Study staff can only first gain access to the admin web portal if granted by a study or site administrator. Their assigned user role will determine their permissions to perform different actions and even view PHI. Email notifications are sent from the system (without the need to login) when: (1) a staff member requests to reset their password, (2) role assignments to a study are made, (3) an event/visit that staff are scheduled to work is nearing, (4) a new task is assigned to a staff member, or (5) they are designated as a staff member to receive alerts of positive test results. All participant communications are performed using secure messaging through the message center (inbox) implementation within the mobile app. If the mobile app is not utilized by a study, communications are sent as standard email or text messages to participants.

Mobile App: The mobile app, developed natively for iOS and Android platforms and available for free in the App Store and Google Play Store, is an optional feature the study can utilize for self-scheduling,

communication, photo uploads, and updating contact information. The study will indicate during the initial setup within the admin web portal whether the participant mobile app is utilized or not. If the app is utilized, participants will receive download instructions after their information is entered into the admin web portal. Only participants listed in an active study who validate their email or phone number against the contact information listed in the admin web portal will be able to proceed into the app. For validation, the app uses both traditional form authentication as well as social login (Facebook and Google). The social login feature will only work if the email associated with either social account matches the contact information within the admin web portal. The app does not request anything other than basic information from these authentication services. Participants cannot “remember” their password on the mobile device for automatic logins to ensure privacy. All participant data and activity status is maintained within a secure and encrypted SQL Server database. To create the connection between the admin web portal and the mobile app, each participant is assigned a unique ID within the application, which is associated with their login credentials. When a participant has been successfully authenticated through the mobile app, the admin web portal will send their specific information to their phone through the established secure session (web APIs using SSL). The app will not store the information presented locally on the phone. Local data storage is used only for storing some minimal non-PHI information, such as app settings. The mobile app implements an automatic logout when there is inactivity for more than three minutes. If a participant should need to re-download the app on a new device, login and password authentication will be required again.

The mobile app has push notifications that are primarily used for reminders and notifications of new messages. Push notifications displayed on the participant’s phone will be generic in nature and not contain any PHI. Reminders and notifications within the mobile app inbox will also be generic in nature, with any message containing sensitive information requiring a pin, established during registration as a secondary authentication, to open within the mobile app. Firebase cloud-messaging service is used as a communication channel for these notifications. No PHI is passed through Firebase. Push notifications are customizable in the study setup, and samples of system notifications include: “You have a new message in your inbox,” “You have an upcoming event for March 7, 2018,” and “You have a pending task.”

Web Service: A web service will also be hosted on the web server. This service is used by the mobile application to retrieve and store data. The service will utilize secure socket layer (SSL) for communication.

7.5 Data Quality Assurance

Investigators receiving federal funding must adhere to the Code of Federal Regulations (CFR) to protect research participants and produce reliable study information. Sites participating in research sponsored by the NIMH need to have an internal quality assurance (QA) plan that will identify problems and correct errors in research study records.

7.6 Role of Data Management

UNC will provide instructions concerning the recording of study data on CRFs, and the entry and transmission of the data, and administration and transmission of CASI data.

7.7 Study Site Monitoring and Record Availability

Site monitors at UNC may visit participating study sites to review a selected portion of the individual participant records, including assent/consent forms, CRFs, and supporting source documentation to ensure the protection of study subjects, compliance with the protocol, and accuracy and completeness of records. Regulatory files, as required, will also be inspected to ensure that regulatory requirements are being followed.

The site investigator will make study documents (e.g., assent/consent forms, case report forms) *and pertinent hospital or clinic records* readily available for inspection by the local IRB, the central IRB, the site monitors, the NIMH, the Office for Human Research Protections (OHRP), or the sponsor's designee for confirmation of the study data.

8.0 PARTICIPANT MANAGEMENT

8.1 Tracking Participants / Follow-up

All subjects will be contacted before each follow-up study visit/assessment (i.e., enrollment, 2-week visit for Arm 2 participants, one-month, three-month, and six-month time points). Multiple contact methods will be used for youth who are difficult to reach (e.g., mail, alternate phone numbers, e-mail, text message, Facebook). Doximity, a HIPAA compliant app, may be used to call participants. Subjects will be asked whether or not messages can be left for each of the phone numbers that they provide. They will be informed that messages will not contain any information regarding the nature of the project. The SMART participant management system will be used.

8.2 Compensation

Technical pilot participants: Compensated with \$75 for participation.

RCT participants: Compensated with \$50 at enrollment visit, \$50 for completing baseline modules (Arm 2 participants only), \$50 for the 2-week visit (Arm 2 participants only), \$25 at the one-month visit, \$25 at the 3-month visit, and \$50 at the six-month visit. Participants who do a qualitative interview will receive an additional \$50. (\$200-300 total). Compensation will be provided in person, sent digitally or can be mailed to subjects, if allowed by the SRV.

8.3 Intervening on "Social Harms"

We identified the following items as possible risks to subjects and describe how we plan on addressing those risks:

- 1) Breach of Confidentiality: A potential risk to participants is violation of confidentiality. We will take the utmost caution to protect the confidentiality of all responses. We will minimize this risk by maintaining confidentiality and discretion throughout the usability testing, field testing and RCT. Files – audio, paper and electronic– will not have any identifying information about the study participants and will be tracked through a unique SID. All audio recordings will be downloaded and stored on a password-protected, encrypted computer in locked offices at UNC-CH and subsequently transferred to UNC encrypted servers. Transcription of audio files will be conducted using a HIPAA-compliant transcription service. Any names mentioned in the audio files will be redacted during transcription. Interview transcripts will be kept on UNC secure servers. Analysis of transcripts will be conducted on a password-protected, encrypted computer. Hard copies will be kept in locked files. This research specifically targets a vulnerable population, children (YMSM ages 16-17). We will take every available step to minimize the risk of identifying/linking data being subpoenaed, stolen, or inadvertently released. First, the Tough Talks has acquired a Certificate of Confidentiality from the NIH.. Second, the study will safeguard against the risk of the linking information being stolen by keeping such information in a locked Excel spreadsheet on a secure server at UNC to which only essential study personnel who have completed CITI certification for human subjects research ethics training (<http://citiprogram.org>) will have access. We have also included numerous features to ensure app security and privacy. All relevant app communications (e.g. those between participants or those between participants and staff) will be secured via industry standard encrypted SSL communications links. These connections will ensure that all communications are inaccessible to unauthorized third parties. Furthermore, the app can be updated regularly to address any unforeseen security updates to the software libraries underlying the secured communication links. Beyond encrypting communication, we users will need to log in with a username and password to access the app, even if the use of their phone is “unlocked”. This will allow the user to share their phone generally with others without granting access to Tough Talks. These software security solutions will provide the layers of both communications security and physical access security to ensure that only authorized users have access to the information stored on the phone as well as the information being shared over communications links. We will take special care to ensure that Tough Talks addresses participant privacy. We have chosen the app name, Tough Talks, because it does not relate to health care and is therefore designed to be non-stigmatizing and uninterpretable by anyone observing a participant using the app on their mobile phones. During app onboarding, study staff will assist youth in choosing a discreet and anonymous username. Moreover, mobile phone screens themselves are also constructed to prevent surreptitious observation.
- 2) Emotional discomfort: It is possible that the study may precipitate discomfort and/or an emotional response when YMSM answer questions about potentially sensitive topics such as HIV disclosure. Further, participants may feel embarrassed about discussing sensitive issues. All participants will be told during the informed consent process that their participation is voluntary and that they can choose to stop participating at any time without any consequences. Based on our experiences using similar data collection methods with YMSM in past studies, the likelihood and seriousness of this risk is minimal and we will strive to create a safe and comfortable environment for all study participants.

3) Discomfort during collection of blood specimen: The risk of discomfort due to blood sample collection is considered minimal. Physical harms are minimal. Blood samples will be collected based on best clinical practices in each of the SRV sites by trained staff. Subjects could experience dizziness, diaphoresis and nausea associated with the procedure but in prior clinical studies using blood sample collection, adverse events have been rare.

All sites have specific policies governing the treatment of human subjects. These policies specify that medical and psychological assistance will be available in the immediate environment in the event a participant should experience any adverse reactions resulting from study procedures.

While participants will be informed that they may refuse to answer any question at any time, responses or reactions to certain questions may indicate distress on the part of the participants. If at any time during the study a participant divulges that they are at risk for harm, including but not limited to being abused or experiencing violence, if harm is suspected or likely, or if the participant states they are suicidal/homicidal, measures will be taken to ensure their safety. Reporting will be done as appropriate to the situation and the legal statutes, including reporting to child protection agencies or other appropriate agencies, and referrals will be provided to appropriate support, counseling, or treatment resources.

8.4 Criteria for Premature Study Discontinuation

The principal investigator has the authority to withdraw any participant at any time if in their opinion it would be in the best interest of the participant. The participant will be informed of this withdrawal and explained the rationale. Withdrawal will be documented in the study tracking system.

Subjects will be prematurely discontinued from the study if any of the following occurs:

- The subject withdraws consent/assent;
- The study is cancelled by the *NIH*;
- The study is cancelled for other administrative reasons;
- The subject becomes incarcerated or placed in detention during the study; or
- Death of the subject.

Participants may end their participation in the study at any time. No further data collection will occur from the date the decision is made to permanently discontinue the subject from the study. Participants who experience distress during the study while in the study site clinic will be offered counseling on site. Participants who experience distress during the study and do not come to the clinical site for a visit will be provided a list of community referrals via phone or e-mail. Any unexpected adverse events that meet the new safety information reporting criteria will be immediately reported to the UNC-CH IRB and the respective sites' IRBs if applicable. The *Study Stop and Adverse Event Forms* will be completed at this time.

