4.4 Informed Consent

Informed consent/assent: Individuals interested in screening for study participation will be consented/assented for screening after reading information about the study and screening procedures. Those who meet initial eligibility criteria and schedule an enrollment visit will undergo a detailed informed consent/assent process where study staff will explain all study procedures and answer questions concerning the study and consent/assent process. The research staff member will give the participant as much time as needed and will address any questions or concerns they may have. The research staff member will ask the participant questions to gauge comprehension. The consent/assent form describes all study procedures, including confidentiality and privacy; information about potential risks, discomforts, and benefits of participation; a section on HIPPA consent for medical chart abstraction; and information regarding who they can contact with further questions. It also states that participation is voluntary, that participants may decide to not take part or to withdraw from the study at any time without penalty or loss of any benefit to which they might otherwise be entitled, and that study participation is in no way related to being able to access or continue getting care or services at any participating study site. Participants can refuse to answer any question and can withdraw from the study at any time. The PIs, Co-PIs, or designee at each site will review all informed consents and assents.

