9.0 MONITORING UNTOWARD EFFECTS ASSOCIATED WITH OR RESULTING FROM STUDY

Site research staff must first follow both the UNC IRB and their own IRB's procedure for reporting and managing untoward effects.

There are three types of untoward effects to be identified: 1) those related to the participant, 2) those related to the study staff, and 3) those related to the neighborhood/community (*if applicable*).

First, the study will catalogue any untoward effect related to the participant. Reporting is required for occurrences including social harms, psychological distress, and serious life-threatening events such as suicide attempts. These may be immediately apparent to the study staff, such as the participant's emotional upset state requiring referral for counseling; or they may be delayed and reported later to study staff, such as physical harm to an individual for having participated in the study. Study staff will notify the UNC/Duke teams via secure email with a subject line stating that immediate response is necessary. Study staff will be briefed with best practices and trainings on the scope of possible untoward effects and how to report events.

Second, study staff may encounter untoward events during sessions that personally affect them. Training and guidance will seek to minimize this risk. Nonetheless, an assessment of the cost of conducting this study must include cataloguing these events as well. The UNC/Duke team will be notified of these events so that they may be immediately addressed, evaluated, and then modify guidance or expanded to minimize similar risk to other study staff.

Third, a critically important area that any community-based study intends to evaluate is the impact, including untoward effects, of the project on the community. This will be done informally for this protocol with untoward events being reported to the protocol team.

All untoward effects/adverse events/unanticipated problems will also need to be reported to the UNC IRB if they meet all three of the following criteria:

"Unanticipated problems involving risks to subjects or others" (UPIRSO) refers to any incident, experience, or outcome that:

- 1) is unexpected (in terms of nature, severity, or frequency) given (a) the research procedures that are described in the protocol-related documents, such as the IRB-approved research protocol and informed consent document; and (b) the characteristics of the subject population being studied;

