- 2) is related or possibly related to a subject's participation in the research; and
- 3) Suggests that the research places subjects or others at a greater risk of harm (including physical, psychological, economic, or social harm) than was previously known or recognized.

Events that meet the criteria for an UPIRSO and are also serious adverse events should be reported to the UNC IRB within one (1) week of the investigator becoming aware of the event. Any other events that meet the criteria for a UPIRSO should be reported to the IRB within two (2) weeks of the investigator becoming aware of the problem.

If the report cannot be completed in its entirety within the required time period, a preliminary report should be submitted. The report should be amended once the event is resolved and/or more information becomes available.

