10.1.3 RCT

Conduct a combined efficacy/effectiveness trial to compare the intervention delivered online, in the clinic, or SOC clinic disclosure messaging. The primary outcome of HIV viral suppression will be assessed at six months. We will also assess intervention efficacy on a panel of self-reported outcomes including CAI, STI infections, disclosure behaviors, intentions and self-efficacy assessed at baseline, 3 months, and 6 months. Cost effectiveness of both intervention arms will also be assessed.

The primary analysis will be based on intention-to-treat principles, where all participants are assumed to have followed their randomized assignment; secondary analyses will account for observed intervention completion. Additionally, we will develop a mathematical model to estimate secondary HIV transmissions and potential transmissions averted as a result of the intervention's effect on viral suppression and CAI with susceptible partners.

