11.7 Prisoner Participation

NIMH has concluded that this protocol does NOT meet Federal requirements governing prisoner participation in human subjects research and should NOT be considered by local IRBs for the recruitment of prisoners. Subjects enrolled who subsequently become incarcerated or are placed in detention may not continue study participation. Study visits cannot be conducted during the period of incarceration or detention.

11.8 45 CFR Parts 160 and 164 Standards for Privacy of Individually Identifiable Health Information ("Privacy Rule" Pursuant to the Health Insurance Portability and Accountability Act - HIPAA)

Each site is responsible for adherence to their individual institution's HIPAA policies and procedures.

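### Section 8.4 ends all data collection after any permanent discontinuation, so a participant withdrawn by the investigator without revoking consent can lose a six-month viral load obtainable from the chart

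*Combined protocol and SAP*

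**What the plan says.** Section 8.4 opens with a discretionary route out of the study, judged by the participant's own interest: "The principal investigator has the authority to withdraw any participant at any time if in their opinion it would be in the best interest". It then lists further reasons for discontinuation: withdrawal of consent or assent, cancellation of the study, incarceration or detention, and death. One data rule follows: "No further data collection will occur from the date the decision is made to permanently discontinue the subject from the study". It makes no distinction by reason or by who took the decision. The "Study Stop and Adverse Event Forms" are completed at that time.

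Other sections bear on this:

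- **Analysis.** Section 10.1.3 states: "The primary analysis will be based on intention-to-treat principles". Section 10.3.3 (primary analysis) sets the endpoint as viral suppression at six months.
- **Source of the endpoint.** Sections 5.1 and 10.3.3 look first for a chart value from the two months before the six-month visit. Failing that, a study blood draw or a routine-care value up to three months after the visit is used.
- **Consent.** Section 4.4 says the form contains "a section on HIPPA consent for medical chart abstraction".
- **Safety.** Section 9.0 says of harms to participants that "they may be delayed and reported later to study staff". For a report to the UNC IRB that cannot be completed in time, it asks for a preliminary report and adds: "The report should be amended once the event is resolved and/or more information becomes available".
- **Missing data.** Section 10.4 plans an analysis of participants with the endpoint, then analyses with imputed endpoints. Section 10.3.3 allows censoring weights if loss exceeds 15% or differs by arm.

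**The concern.** A full stop on data collection is right when a participant revokes consent. An investigator-decided withdrawal is different: the participant may have revoked nothing, and the chart may later hold the value the primary analysis needs. No other section restores collection for that person.

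Two things are at stake. First, the missing endpoint may be informative. Participants removed in their own interest may differ in suppression from those who stay. Some reasons for removal, such as distress during virtual disclosure practice, can arise only in the two Tough Talks arms. If those removed are less often suppressed, the observed rate in their arm is too high.

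Second, staff handling an open event have two instructions that are hard to read together. Section 8.4 closes data collection on the date of the decision, while section 9.0 anticipates late-emerging harms and amended reports.

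**Working it through.** **1. The plan's own sample size.** Inputs from section 10.2.3: suppression 0.66 against 0.88, two-sided alpha 0.05, 80% power, 15% loss, 66 per arm. SOC is taken to stay at its baseline rate of 0.66.

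Evaluable n per arm (pooled variance, no continuity correction) = [1.960 × √(2 × 0.77 × 0.23) + 0.842 × √(0.66 × 0.34 + 0.88 × 0.12)]² / 0.22² = 56.2, so 57.

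- 57 × 1.15 = 65.6, so 66, the stated figure.
- 57 / 0.85 = 67.1, so 68, within 2 of it.
- At 66 × 0.85 = 56.1 evaluable per arm, power is 0.799. With all 66 observed it is 0.860.

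The sample size reproduces, and nothing in this point changes it. A few withdrawals fall within the 15% allowance, so the issue is bias rather than power.

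**2. Who is affected.** Set side by side, the sections give:

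- *Not finishing the app:* section 5.1 provides reminders in Arm 1; it is not a reason for discontinuation.
- *Missing the one- or three-month assessment:* sections 6.5 and 6.6 keep the participant eligible for later assessments.
- *Revoking consent:* section 8.4 stops collection, appropriately.
- *Withdrawal by the investigator:* section 8.4 stops collection, with no exception for chart data.

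Only the last group is at issue. The viral load is lost only if no value in the six-month window was obtained before the decision. The documents give no expected number of such withdrawals.

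**3. Illustrative size.** Assumptions: 66 in one intervention arm with true suppression 0.88, k unsuppressed participants withdrawn from it, none withdrawn from SOC, no other loss, complete-case analysis.

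Observed rate = 0.88 × 66 / (66 − k) = 58.08 / (66 − k).

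- k = 1: 58.08 / 65 = 0.8935, up 1.35 points; the risk difference moves from 0.220 to 0.234.
- k = 2: 58.08 / 64 = 0.9075, up 2.75 points; the risk difference is 0.248 (0.2475).
- Two withdrawn, one of them unsuppressed: 57.08 / 64 = 0.892, up 1.2 points.

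If one unsuppressed participant is also withdrawn from SOC, its rate becomes 43.56 / 65 = 0.670, and the risk difference is 0.8935 − 0.6702 = 0.223. Most of the bias then cancels.

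**4. What the planned methods recover.** Complete-case analysis drops these participants. Last value carried forward, which section 10.4 gives as an example, would use a value from before the withdrawal. Censoring weights are optional and their covariates are not named. They help only so far as the chosen covariates explain both withdrawal and suppression. None of these replaces an observed chart value.

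**The case against.** The strongest reply is that this is a rare route in a minimal-risk trial. Section 8.3 rates the likelihood and seriousness of emotional discomfort as minimal and ties it to sensitive questions, which all three arms answer. Withdrawal because of harm is an inference from the best-interest wording. The plan allows for 15% loss, imputes missing endpoints and can weight for differential censoring. A chart value is not guaranteed either, since remote participants enrol nationwide and other sources are permitted. Much of this stands. It limits the size of the problem but does not explain why a value available without a visit should be forgone when nobody has revoked permission.

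Five stronger readings are tempting, and the documents do not support them:

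- *No one can stop the app and stay in follow-up.* They can. Sections 5.1, 6.5 and 6.6 keep such participants in, and the analyses by observed completion in sections 10.1.3 and 10.3.3 presuppose it.
- *Section 9.0 requires every event to be followed to resolution.* It does not. The amendment duty concerns incomplete IRB reports of unanticipated problems. Section 8.4 itself provides counselling or referral, immediate reporting of qualifying events and completed forms. The tension between the sections is therefore narrow.
- *Sections 8.4 and 11.7 conflict on detention.* Section 11.7 does say "Study visits cannot be conducted during the period of incarceration or detention", which alone might suggest a temporary pause. The sentence before it bars detained participants from continuing in the study, which agrees with 8.4.
- *The weights use baseline data only.* Section 10.3.3 names baseline suppression for the treatment weights and leaves the censoring covariates open.
- *The bias could be a large share of the planned effect.* Withdrawing 4 or 6 unsuppressed participants would add 5.7 or 8.8 points (58.08 / 62 = 0.937; 58.08 / 60 = 0.968). But the arm has only about 8 unsuppressed participants (66 × 0.12 = 7.9), so half or more would have to be withdrawn, with none from SOC.

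**Conclusion.** The point holds in a limited form. Section 8.4 applies a rule suited to revoked consent to investigator-decided withdrawal as well. It thereby gives up endpoint data that an intention-to-treat analysis should keep where permission remains. The missingness may be related to arm and outcome, and the planned methods address it only in part.

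The effect is probably small: 1.35 to 2.75 points on one arm's suppression rate for one or two withdrawals, against a planned 22. That illustration rests on assumed counts, on all those withdrawn being unsuppressed, and on none being withdrawn from SOC. The documents give no withdrawal rate and do not establish a link between distress and non-suppression. The case for change rests on how little it costs to avoid the loss, not on a demonstrated large bias.

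**What to change.** In section 8.4:

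- Limit the stop on data collection to withdrawal of consent or authorisation, death, study cancellation, or cases where the rules on detention require it.
- State that after an investigator-decided withdrawal, unless the participant revokes chart authorisation, the six-month viral load is still abstracted from the chart within the existing window.
- State that open untoward-event reports may still be updated as section 9.0 describes.

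The investigator's authority to withdraw a participant stays as it is. Check that the consent and authorisation wording covers abstraction after such a withdrawal. Section 4.4 shows only that a chart-abstraction section exists, and the form was not among the material reviewed.

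The cost is a wording change in 8.4, possibly a sentence in the consent form, an IRB modification and a little chart abstraction. It needs no new visits, no blood draws and no change to 66 per arm.
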